- 1) Those participants who are randomized to the active Picture This! savoring condition will be asked to use their Smartphones to take at least two photographs each day for 3 weeks of something that brings them joy or peace and to upload their pictures daily to a drive accessed by study staff (instructions for each condition may be found in Appendix A). Each evening, they will be directed to

complete an online exercise in which they review the photograph(s) taken that day. They are also asked to complete several questions via an internet survey.

- 2) Participants randomized to the Picture This! Plus Social Sharing will do everything as described for the Picture This! group. In addition, each week, they will be directed to share the photos they took during the prior week with a friend or family member (see script provided in Appendix B).
- 3) Those participants who are randomized to the active control condition (Document This!) will also be asked to take 2 photographs each day using a Smartphone and to upload their pictures daily to a drive accessed by study staff. Rather than focusing on and capturing a photo of stimuli that evokes positive emotion, however, they will be directed to take pictures of things in their lives or surroundings that are representative of a “day in the life”. Like the participants in the Picture This! and Picture This! Plus Social Sharing Groups, they will also be asked to complete an online exercise each evening in which they review their documentary photos each evening and also asked to complete a series of questions via an internet survey.
- 4) Finally, participants randomized to the passive control group will NOT be directed to take any pictures during the 3 week intervention period.

All research participants in all 4 groups will be asked to complete a weekly online survey asking about whether they shared the pictures they took as a part of the study or as a part of their regular life (see Appendix F).

At the end of the intervention, all subjects will be provided a list of local mental health resources and will also be provided with the instructions for all 3 picture taking conditions (should they wish to implement any of the other exercises on their own time).

2. Identification of Subjects:

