- 13) **Rosenberg Self Esteem (RSE)** is composed of 10 statements regarding general notions of self perception. The respondent is directed to indicate how strongly he/she agrees with the statement (i.e., I take a positive attitude toward myself) using a 7 point Likert scale.
- 14) **Scale of Physical Symptoms** consists of a list of 9 physical symptoms including shortness of breath, runny or congested nose, and chest or heart pain. Participants indicate how often they've experienced such symptoms over the past month using a 7 point scale, ranging from Not at All to Frequently.
- 15) **Pittsburgh Sleep Quality Inventory (PSQI)** is a self report measure designed to assess sleep difficulties, sleep quality, and to gather data regarding bedtimes, waking times, and number of hours slept.
- 16) **Social Connectedness Scale (SCS)** is an 8 item scale that assesses an individual's sense of connection and disconnection to society, peers, etc. Two additional items have been added to the original scale to assess connection/disconnection to nature and to a spiritual/religious community.
- 17) **MOS Social Support Scale** is composed of 19 statements describing possible supports (e.g., advice, information, help with chores) to which the respondent is asked to indicate how often each is available to him/her.
- 18) **Perceived Stress Scale (PSS)** asks respondents to indicate how often in the past month they have felt stressed, nervous, unable to cope, etc., using a 5 point Likert scale.
- 19) **Life Events Scale (LES)** requires individuals to indicate which of the possible positive negative life events he/she has experienced during the most recent 6 months.
- 20) **Emotion Socialization Scale of the Emotions as Child Scale (EAC)** was modified slightly by Garside and colleagues to include both mother and father responses to the respondent's emotional displays as a child. Using a 7 point Likert scale, participants indicate how often each parent responded to sadness, for example, with 15 different possibilities.
- 21) **Emotion Regulation Questionnaire (ERQ)** directs participants to indicate how strongly they agree or disagree with 10 statements describing ways people typically regulate or manage emotion.
- 22) **Ten Item Personality Inventory (TIPI)** is a very brief measure of personality. Participants are asked to indicate the extent to which each of the statements describes them.

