Participants in all 3 active control groups will also be given the opportunity to choose whether they would like to be reminded to take photographs via text message or email. The text messages will be generated from the study Gmail account. Participants are reminded in the consent form that they are responsible for any charges accrued for receiving text messages if they choose that option.

At the end of each 7 day period, participants in the active **Picture This! Plus Social Sharing Group** are asked to share their photographs with a friend, relative, or loved one of their choice. Email reminders to complete the sharing exercise will be provided. The sharing should be done in person, rather than via email or over the phone. The participant may choose with whom to share the pictures and may decide to show the same person his/her pictures each week for the 3 week period or may decide to share with different people each week or some combination thereof. Scripts are provided to guide the participants (see Appendix B). Given that the participants may have taken many more than the required photographs during the prior week for this project, the time it takes to share them will vary. However, participants will be asked to limit the interaction to approximately 15 minutes. Participants in the Picture This! group and the Document This! control group are not asked to share their photographs. Following the sharing activity, participants in the Picture This! Plus Social Sharing Group are asked to answer 5 questions online, again following a link they will have received by email (see Appendix E). To keep payment equal, all other participants are also asked to complete a weekly survey of 5 questions about taking and sharing photographs.

At the completion of the 3rd 7 day period, all participants will be invited back into the laboratory to complete an exit questionnaire packet and to repeat the 2 computerized tasks they completed at baseline. This packet will include the following measures:

- 1) Demographics and Psychiatric History Follow-up
- 2) Modified Differential Emotion Scale (MDES)
- 3) Self-Other Four Immeasurables Scale
- 4) Ambiguous Situation (with 10 novel statements)
- 5) Santa Clara Brief Compassion Scale
- 6) Gratitude Questionnaire (GQ-6)
- 7) Cognitive Style Questionnaire Short Form (CSSF)
- 8) Beck Depression Inventory – II (BDI-II)
- 9) State-Trait Anxiety Inventory (STAI)
- 10) Savoring Beliefs Inventory (SBI)

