- 11) Carolina Empirically Derived Mindfulness Inventory (CEDMI)
- 12) Brief Satisfaction with Life Scale (BSWLS)
- 13) Rosenberg Self Esteem
- 14) Scale of Physical Symptoms
- 15) Pittsburgh Sleep Quality Inventory (PSQI)

- 16) Social Connectedness Scale (SCS)
- 17) MOS Social Support Scale (MOS)
- 18) Perceived Stress Scale (PSS)
- 19) Life Events Scale (LES) Respondents will be asked to consider the time that has elapsed since baseline (which should be approximately 4-5 weeks).
- 20) Emotion Regulation Questionnaire (ERQ)
- 21) TOSCA-3 with 16 novel scenarios
- 22) Irritability Question
- 23) Intervention Assessment – 5 questions created by the project staff to assess participant satisfaction with prescribed exercises and to elicit suggestions for improvement.

The following compensation/incentive schedule for completing questionnaires and participating in the study will be utilized:

- Participants who complete the baseline questionnaire packet and computer tasks will be compensated \$10 or be provided with class credit via the psychology subject pool.
- Participants who complete the exit questionnaire packet and computer tasks will be compensated \$19 or be provided with class credit via the psychology subject pool.
- Participants will be compensated \$1/day for completing the nightly online questions for a potential total of \$21.
- Participants will be compensated \$1/each weekly survey completed for a potential total of \$3.

Hypothesized Outcomes

H1: Participants in the Picture This! (PT) and Picture This! Plus Social Sharing (PTPSS) conditions will evidence increased well-being as indexed by measures of: a) depressive symptoms, b) positive affect, c) savoring beliefs, d) mindfulness e) life satisfaction, f) self esteem, g) gratitude, h) physical health and sleep quality, and i) perceived social support, relative to participants in the active control and no picture control conditions.

H2: Participants in the Pictures This! Plus Social Sharing will demonstrate greater improvement in perception of social support than those in any other condition.

Mediators of Change.

H3: Participants in the PT and PTPSS conditions will show significant changes in automatic cognitive processes including attentional biases, interpretational biases, and cognitive style assessed via behavioral tasks and self report.

H4: Changes in the aforementioned cognitive processes will account for the positive changes in mental and physical health.

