H5: Participants in the PS and PTPSS conditions will demonstrate significant changes in behavioral indicators of attentional shifts. We anticipate participants in the active experimental conditions will a) take increasingly more photographs over the course of the intervention and b) will include more social behavior as the focal point.

Supplementary Analyses

H6, exploratory: In order to inform future implementation and potential mechanisms of change, we will examine photographic content. We also anticipate changes in the quality of the photographs over the course of the intervention for the participants in both active experimental conditions. It is possible that the photographic content would be judged by independent raters to be increasingly positive over the course of the intervention. Alternatively, it is plausible that as the participant's ability to attune to the positive cues in the environment

develops, the capacity to find joy in even the most mundane objects/moments will be evident in photographs judged by independent raters to have less objectively rated positive appeal.

H7: Depressive symptoms will moderate the associations between intervention participation and daily positive affect, life satisfaction, and perceived social support, such that participants with higher levels of pre-intervention symptoms will show larger improvements in outcomes in the intervention conditions.

H5b and H6 are straightforward between-groups analyses, for which we will use ANOVA to test for significant differences between groups on the outcomes of interest. H1-H3 and H5a will be tested using mixed-factor ANOVA, with condition as a between-subjects factor and the within-subjects factor being pre-intervention measure of the outcome of interest included as predictors of the post-intervention outcome (e.g., perceived social support). Planned contrasts will probe for significant differences in effects between the experimental conditions and each control condition, as appropriate. H7 will be tested using two additional predictors, the main effect of the individual difference of interest (e.g., depressive symptoms) as well as the interaction between the individual difference and condition. H4 (mediation) will be tested using the most up-to-date evidence for bootstrapping estimates (see Hayes; Preacher & Hayes, 2008).

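### H2 predicts that Picture This! Plus Social Sharing beats every other arm, but the stated planned contrasts leave out its comparison with Picture This!

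*Combined protocol and SAP*

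**What the plan says.** Under Hypothesized Outcomes, H2 reads: "Participants in the Pictures This! Plus Social Sharing will demonstrate greater improvement in perception of social support than those in any other condition". The trial has four arms, so this covers three comparisons: PTPSS against PT, against Document This!, and against the passive control.

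The analysis paragraph after H7 (Supplementary Analyses) tests H1 to H3 and H5a by mixed-factor ANOVA with condition as the between-subjects factor. The only contrasts it names are in this sentence: "Planned contrasts will probe for significant differences in effects between the experimental conditions and each control condition, as appropriate".

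The documents are clear about which arms are controls. H1 sets PT and PTPSS together "relative to participants in the active control and no picture control conditions", and H6 speaks of changes "for the participants in both active experimental conditions". The description of the four conditions calls Document This! the active control.

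The same description says how PT and PTPSS relate: "Participants randomized to the Picture This! Plus Social Sharing will do everything as described for the Picture This! group". PTPSS adds weekly scripted sharing in person. Under Testing Procedure, "Participants in the Picture This! group and the Document This! control group are not asked to share their photographs".

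**The concern.** H2 is the only hypothesis that singles out the sharing component. Its distinctive part is PTPSS against PT, because both arms do the same picture and savoring exercise and differ only in being assigned to share. A contrast of PTPSS with either control mixes the exercise with the sharing. Without the PT comparison, H2 largely repeats the PTPSS half of H1(i).

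An analyst who runs only the stated contrasts could find PTPSS ahead of both controls on social support and report H2 as supported, although the whole gain might come from the exercise that PT also receives. The plan does not say which combination of results counts as support for H2.

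**Working it through.** The plan gives no alpha, effect size, SD, allocation ratio or dropout for H2, so it has no figure of its own to reproduce. The main check is of the text; the arithmetic only illustrates the consequence.

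**Step 1. Comparisons H2 needs against contrasts stated.**

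| H2 comparison | Stated contrasts read pairwise (2 experimental × 2 control = 4) | Stated contrasts read as pooled experimental arms v each control (2) |
|---|---|---|
| PTPSS v Document This! | included | not included |
| PTPSS v passive control | included | not included |
| PTPSS v PT | not included | not included |

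On the pairwise reading, the missing comparison is the difference of two stated ones: PTPSS − PT = (PTPSS − control) − (PT − control). The model can therefore estimate it, but the plan states no test of that difference. On the pooled reading it cannot be formed from the stated contrasts at all.

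**Step 2. Inputs for the illustration.** Identification of Subjects gives approximately 240 to be recruited. The rest is assumed: equal allocation (240 / 4 = 60 per arm), two-sided 0.05, both controls at 0, and effects in SDs of the analysed score. A second case of 48 per arm supposes a 20% loss (60 × 0.8).

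**Step 3. A single contrast.** The standard error is √(2/n) SD.
- At n = 60: √(2/60) = 0.183. A true difference of 0.5 SD lies 0.5 / 0.183 = 2.74 standard errors from zero. The critical value is 1.97 (236 df), so power is about 78%.
- At n = 48: √(2/48) = 0.204 and 0.5 / 0.204 = 2.45, so power is about 68%.
- The 95% confidence interval half-width is about 1.97 × 0.183 = 0.36 SD at n = 60 and 1.97 × 0.204 = 0.40 SD at n = 48.

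**Step 4. Joint results.** These were simulated with 400,000 trials per setting and a pooled variance. PTPSS is fixed at 0.5 SD above both controls, with 60 per arm.

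| Result | PT at 0 (sharing adds 0.5 SD) | PT at 0.5 (sharing adds nothing) |
|---|---|---|
| PTPSS beats both controls | 66% | 66% |
| PTPSS beats PT | 78% | 2.5% |
| Four-group F test significant | 81% | 91% |

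The first row is equal by construction, since PT does not enter those contrasts. The F test is not directional and does not isolate the pair.

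**Step 5. Reading the control contrasts side by side.** Suppose sharing adds nothing and PT and PTPSS both gain 0.3, 0.4, 0.5 or 0.6 SD (60 per arm). PTPSS beats both controls while PT fails to beat both in about 13%, 18%, 17% or 10% of trials. Counting only trials in which PT beats neither control, the figures are about 8%, 8%, 5% and 2%. If PT is at 0 and PTPSS at 0.5, the first pattern appears in about 65%.

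**Step 6. Power if all three H2 comparisons are required.**
- PT equal to the controls, sharing adds 0.5 SD: about 58% at 60 per arm and 45% at 48. The two control contrasts jointly (66%) are a tighter limit than PTPSS versus PT (78%).
- PT 0.5 SD above the controls, 60 per arm: about 19%, 37%, 59% or 78% for a sharing effect of 0.2, 0.3, 0.4 or 0.5 SD. Here PTPSS versus PT is the limit.

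**The case against.** The best defence is that H2 itself fixes the comparators and the direction, the model has condition as a factor, and the contrast sentence is a general one covering several hypotheses that closes with a qualifier about appropriateness. A careful analyst would run PTPSS versus PT. This stands in part: nothing in the design or data prevents the comparison. But the qualifier gives discretion over which experimental-versus-control contrasts to run; it does not add one between two experimental arms. Nor does Testing Procedure's one loose use of a control label for all three picture-taking groups make PT a control, since read literally it would make PTPSS a control too.

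Two stronger readings are tempting. A reader might infer that the trial cannot test the effect of sharing. The documents do not support that, because the planned model estimates PTPSS minus PT directly. A reader might also infer that the stated contrasts say nothing about sharing. That goes too far: read pairwise they include PT against each control, and the side-by-side pattern is far more common when sharing works (about 65%) than when it does not (10 to 18%). It is informative, but it is not a valid test of the difference, and its error rate varies with the size of the shared gain.

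**Conclusion.** The point holds as a mismatch between H2 and the stated contrasts. H2 needs three comparisons; the stated set holds two of them at most and omits the one that isolates assigned sharing. It should be fixed before analysis.

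This conclusion rests on the text alone. The percentages rest on assumed arm sizes, alpha and effects. In particular, 66% should not be read as the plan's error rate for H2: it is the chance of a result that looks like support when sharing adds nothing, under one assumed set of effects and only if H2 is judged on the control contrasts.

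**What to change.** Add to the analysis paragraph, for H2:

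- PTPSS versus PT on perceived social support is a planned contrast within the model already planned.
- Name the instrument. The MOS Social Support Scale is the natural choice, since it "is composed of 19 statements describing possible supports (e.g., advice, information, help with chores" and is collected at baseline and exit. This is an inference: the documents do not tie H2 to a scale.
- H2 is supported only if PTPSS improves more than PT, Document This! and passive control, each at two-sided 0.05. No alpha adjustment is needed because all three are required.
- Report the PTPSS minus PT difference with its 95% confidence interval whatever the result. If PTPSS beats only the controls, do not attribute the result to sharing.
- Describe the contrast as the effect of being assigned to share, because PT participants are not asked to share but are not barred from it. All four groups "complete a weekly online survey asking about whether they shared the pictures they took", whether for the study or in ordinary life. Report sharing among PT participants beside the contrast if that form (Appendix F, not in the text reviewed) separates study pictures from others.

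The change is wording only and needs no new visits or data. Its cost is that H2 becomes harder to support, with the power shown in step 6. With an interval of about ±0.36 SD at 60 per arm, a non-significant PTPSS versus PT contrast is not evidence that sharing has no effect, and the plan should say so.
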